6. COLLECTION AND ENDPOINTS

The outcome data are being collected in real-time and stored by UHB’s team (not the research team) between the day the letters were sent out, the 4th of October 2018, until data-lock at 12:00 AM on the 4th of January 2019. The research team’s statistician, [name], will receive the outcome data on the 4th of January 2019 between 8:00 and 13:00 Greenwich Mean Time.

7. DATA NOT CONSIDERED IN STATISTICAL ANALYSES

The other outcomes (refusal to vaccinate and vaccinating at another site) will not be considered in statistical analyses for two reasons. First, participants are required to self-report this information through an online system that was not encouraged by our interventions. Second, these numbers are typically too small to impact our planned analyses, i.e. typically less than 2.5% of participants.

These outcomes will be reported descriptively for each group in the final report. For example: *Of the total number of participants ## refused to take up the vaccination, of which ## were sent the standard letter, ## were sent the social norms letter, ## were sent the authority letter, and ## were sent the combined letter.*

8. HANDLING OF MISSING VALUES

The outcome data will not have missing values as onsite staff vaccinations, the primary outcome, are all recorded routinely at the time of the vaccination. The denominator will comprise all front-line staff working in the hospital on the day of randomization, the 24th of September 2018. Self-reported refusals and self-reported vaccinations at another site are not the primary outcome data but are recorded on the system when available.

No attempt will be made to include staff joining the hospital after the randomization on the 24th of September 2018.

9. SUPPLEMENTARY ANALYSIS

Unknown to the University team who registered the trial and obtained ethical approval, for operational reasons the hospital members of the research team created a fifth group of participants who were sent no letter (n = 898).

A further analysis will be performed to utilize data collected in response to this protocol deviation. Using the information collected because of this deviation, we will compare the uptake of staff in this group to the amalgamation of those who were sent any of the four letters. This will be done by comparing the vaccination rates in these two groups using Fisher's exact test and also by binary logistic regression analysis with the outcome on-site vaccination (0 = No, 1 = Yes) and the following explanatory variables: whether letter sent (0 = No, 1 = Yes), Employment-type (0=Bank, 1=Substantive), Job-Type (1=Medical and dental staff, 2=Nursing, midwifery and health visiting staff, and 4= a combined group composed of Healthcare assistants, other support staff and Scientific, therapeutic and technical staff), Gender (0=Female, 1=Male) and any of the following interactions that are significant: Social Norms x Job type; Social Norms x Gender; Authority x Job type; Authority x Gender; Social Norms x Authority x Job type; and Social Norms x Authority x Gender. (If either of the three-way interactions is included, all the constituent two-way interactions will also be included.)

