Appendix 1.

On the next page are four letter formats. One factor is the presence of an authority figure giving staff access to the vaccinations. The authority figure is [name], the Chief Executive and also a medical doctor. The other factor is the presence of descriptive norms describing the proportions of staff that have been vaccinated in peer hospitals.

Within the examples the highlighted areas indicate where these two factors are active.

GREEN = authority factor.

YELLOW = norms factor.

Short Title: An improvement project around staffs' influenza vaccine uptake

Emailed Letters.

Letter one

Dear colleague,

You are invited to take up your free flu jab this season to reduce your risk, and your patients' risk, of getting the flu.

Find out how to get your jab at the Trust, please visit the [] part of the Intranet or ask your line manager.

We appreciate your support in keeping colleagues and patients safe,

Occupational; Health Department

Letter two

Dear name,

I am inviting you to take up your free flu jab this season to reduce your risk, and your patients' risk, of getting the flu.

Last winter, the national expectation was for at least 70% of frontline staff to be vaccinated against seasonal flu. That was achieved at QEHB, with **71.6%**, and at Heartlands, Good Hope and Solihull with **73.5%**. This year, the national expectation is for 75% of frontline staff to be vaccinated.

However, we want UHB to be amongst the very best performers of similar hospitals, so that we maximise protection for our staff and patients. We know it is entirely achievable, with your support, for us to reach or surpass the levels of some of the best performers from last year:

Royal Liverpool & Broadgreen	86.9% of frontline staff vaccinated
Cambridge University Hospitals	84.3%
Birmingham Children's Hospital	82.1%
Leeds Teaching Hospitals	80.8%
Guy's and St Thomas's	79.9%

In the United States 92% of hospital staff receive flu vaccination.

Find out how to get your jab at the Trust, please visit the [] part of the Intranet or ask your line manager.

I appreciate your support in keeping colleagues and patients safe,

Kind regards

Occupational Health Department

Letter three

Dear colleague,

You are invited to take up your free flu jab this season to reduce your risk, and your patients' risk, of getting the flu.

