2. DATA

Data collection is described in protocol (version 2, page 5). However, deviations from the protocol resulted in modifications to some of the data we will have available for the analyses. Table 1 describes the data contained in the data file.

The first deviation occurred because of the four worksites originally planned to be in the trial, three could not take part. This left one worksite in the trial, i.e. Queen Elizabeth Hospital.

The second deviation affects our plans for sub-group analyses. This occurred because the trust records describe job roles differently than stated in the protocol. So instead of the job roles stated in the protocol, staff were stratified by two Employment-Types and four Job-Types.

The third deviation occurred as 898 (10.6%) of the hospital's 8438 staff randomized were allocated to a fifth, no-letter, control group. The remaining 7,540 staff were randomized to the planned four groups in equal numbers (i.e., 1885 participants to each of four groups). We will analyse data in the four groups per the original protocol and this will be the primary analysis. However, we will also carry out a subsidiary analysis to compare the results of this no-letter control group to the letter groups, as described in the below section titled 'Supplementary Analysis'.

Table 1. Data in the project analysis file

Type	Name	Codes
Intervention	Group Number	0 = Standard, 1 = Social Norms, 2 = Authority 3 = Combined, and 4 = No Letter Control
Demographics	Gender	0 = Female, and 1 = Male
	Type of Employment	0 = Bank, and 1 = Substantive
	Job Type	0 = Healthcare assistants and other support staff, 1 = Medical and dental staff, 2 = Nursing, midwifery and health visiting staff, and 3 = Scientific, therapeutic and technical staff (for the analyses, groups 0 and 3 will be combined)
Primary Outcome	Date of vaccination at Trust	DD-MM-YYYY, or blank if the vaccination was never received
Other outcomes (formally self-reported)	Refusal to take up the Vaccination	0 = No, and 1 = Yes
	Vaccinating at a non-trust location	0 = No, and 1 = Yes

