In addition to the primary analysis, a binary logistic regression analysis will be used to predict staff on-site vaccination rate (0 = No, 1= Yes) using all of the following variables: the two main intervention effects (Social Norms and Authority) and their interaction effect, Employment-type (0=Bank, 1=Substantive), Job-Type (1=Medical and dental staff, 2=Nursing, midwifery and health visiting staff, and 4= a combined group composed of Healthcare assistants, other support staff and Scientific, therapeutic and technical staff), Gender (0=Female, 1=Male) and any of the following interactions that are significant: Social Norms x Job type; Social Norms x Gender; Authority x Job type; Authority x Gender; Social Norms x Authority x Job type; and Social Norms x Authority x Gender. (If either of the three-way interactions is included, all the constituent two-way interactions will also be included.)

Figure 1. Time series chart

To achieve Objective 3, secondary analysis will assess the effects of the interventions over time, to examine the hypothesis that the benefits of the interventions may be greater nearer the beginning of the trial than nearer the end.

This effect will initially be assessed by visually examining a time-series chart, such as represented in Figure 1. We will also estimate the time to vaccination within each group to reach 70% vaccination. To do so, Kaplan–Meier rates of survival (i.e. non-vaccination) will be derived, with confidence intervals based on the exponential Greenwood formulation of the standard error. We selected 70% because this was the vaccination target and was achieved by the hospital over the 2017–2018 vaccination season. If a rate of 70% is not achieved in all four groups we will estimate the time to reach 10m%, where m is the largest integer such that the rate in all four groups is at least 10m%. The proportional hazards assumption will be tested by including interactions of each term (the two main intervention effects and their interaction) with log of time since 00:00 on 4th October 2018 in a Cox proportional hazards model.

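### The SAP section 9 regression borrows the Norms and Authority interactions from section 5 without their main effects, so the letter-sent odds ratio can stop measuring any letter versus none

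*Combined protocol and SAP*

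**What the plan says.** SAP section 2 records that 898 of the 8,438 randomized staff were placed in an unplanned no-letter group, and promises that "we will also carry out a subsidiary analysis to compare the results of this no-letter control group to the letter groups". Section 9 states the contrast: "we will compare the uptake of staff in this group to the amalgamation of those who were sent any of the four letters". It is to be examined by Fisher's exact test and by a logistic regression.

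The regression uses "the following explanatory variables: whether letter sent (0 = No, 1 = Yes"), together with employment type, job type and gender. To these it adds "any of the following interactions that are significant: Social Norms x Job type; Social Norms x Gender; Authority x Job type; Authority x Gender", plus Norms x Authority x Job type and Norms x Authority x Gender. A hierarchy rule follows: "If either of the three-way interactions is included, all the constituent two-way interactions will also be included".

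The same six interactions and the same rule appear in the covariate model of SAP section 5. That model, however, always contains "the two main intervention effects (Social Norms and Authority) and their interaction effect". Section 9 lists none of these three terms.

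**The concern.** The list fits section 5, where the four letter groups form a 2 x 2 factorial and the question is whether wording works differently across staff. It does not fit section 9, where the question is whether being sent any letter matters. Three problems follow.

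- **The estimand moves.** Once a Norms or Authority term is in the model, part of the letter effect is credited to it. The letter-sent coefficient then leans towards letters without that wording versus no letter.
- **The answer can depend on coding.** With product columns and no main effect, the job type chosen as reference has no Norms slope of its own. Both the test for entry and the letter-sent odds ratio then change with the reference, which the SAP does not name.
- **Entry may not signal an interaction.** The SAP does not say in which model significance is judged. If it is the section 9 model, a Norms effect that is equal in every job type can enter as Norms x Job type, because no main effect is there to absorb it.

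At stake is the SAP's only covariate-adjusted estimate of sending a letter at all. It could differ from Fisher's test merely because it answers another question.

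**Working it through.** **Inputs from the documents.** The group sizes in SAP section 2 reproduce: 898/8,438 = 10.6%; 8,438 - 898 = 7,540; 7,540/4 = 1,885. Tests are two-sided (SAP section 4). The protocol's sample-size paragraph assumes alpha 0.05.

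**Assumptions.** The SAP gives no Norms or Authority value for no-letter staff. I code both as 0, because protocol Appendix 1 defines each factor as the presence of a feature (for norms: "The other factor is the presence of descriptive norms describing the proportions of staff that have been vaccinated in peer hospitals"). Also assumed: job mix 15/40/45%, no-letter uptake 65% in every job type, no Authority effect, and employment type and gender left out.

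**Hand check of scenario (b): every letter +3 points, Norms a further +3.** No-letter odds are 0.65/0.35 = 1.857.

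- Pooled letters: uptake (0.68 + 0.71)/2 = 0.695, odds 0.695/0.305 = 2.279, OR 2.279/1.857 = **1.227**. SE of log OR = sqrt[1/(898 x 0.65 x 0.35) + 1/(7,540 x 0.695 x 0.305)] = 0.074; 95% CI 1.061-1.419. This is the stated contrast.
- Letters without Norms: uptake 0.68, odds 0.68/0.32 = 2.125, OR 2.125/1.857 = **1.144**. SE = sqrt[1/(898 x 0.65 x 0.35) + 1/(3,770 x 0.68 x 0.32)] = 0.078; CI 0.982-1.334. This is what letter sent estimates once each job type has its own Norms slope.
- With Norms, Authority and Norms x Authority main effects added, letter sent is the standard letter alone (n = 1,885) versus none: OR 1.144, SE 0.086, CI 0.967-1.353.

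With product columns for only two job types, letter sent falls between 1.144 and 1.227. In the reference job type it must still fit Norms and non-Norms letters together.

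**Model fits.** I fitted binomial logistic models to expected counts: letter sent and job type, with or without Norms x Job type. Entry is the power of the 5% likelihood-ratio test within that model (noncentral chi-square, 2 df for product columns, 3 df for one slope per job type). Triplets give the reference as the 15% / 40% / 45% group.

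| Scenario | OR, no interaction | Probability of entry (2 df) | OR after entry (2 df) | One slope per job type: entry; OR |
|---|---|---|---|---|
| (a) Norms +5, other letters equal to no letter | 1.118 (0.967-1.293) | 0.974 / 0.893 / 0.862 | 1.018 / 1.048 / 1.054 | 0.983; 1.000 |
| (b) all letters +3, Norms a further +3 | 1.227 (1.061-1.419) | 0.635 / 0.469 / 0.433 | 1.157 (0.994-1.347) / 1.179 (1.014-1.369) / 1.183 (1.018-1.374) | 0.654; 1.144 (0.982-1.334) |
| (c) all letters +5, no wording effect | 1.256 | 0.05 | 1.256 | 0.05; 1.256 |
| (d) Norms +10 in nurses (the 40% group) only | 1.093 | 1.000 / 0.057 / 1.000 | 1.000 / 1.100 / 1.000 | 1.000; 1.000 |

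In (b), if Norms adds 2 points instead of 3, entry is 0.317 / 0.228 / 0.211; for 1 point, 0.109 / 0.090 / 0.086.

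In (d), a real interaction is almost undetectable when nurses are the reference, because their Norms effect has no column. Section 5's model, which has the main effects, detects it with power 0.99 whatever the reference.

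**Range.** I varied base uptake (40, 50, 65, 70%), job mix (15/40/45, 25/40/35, 10/50/40, equal thirds) and reference, with other letters equal to no letter. A Norms effect equal in all job types enters with probability 0.77-0.99 (+5 points), 0.34-0.68 (+3), 0.17-0.35 (+2) or 0.08-0.12 (+1). For +5 the OR moves from 1.11-1.13 to 1.01-1.07; for +3, from 1.06-1.08 to 1.01-1.04.

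**Second set of assumptions.** With gender in the model, no-letter uptake about 40-48%, a standard letter with OR 1.00 and Norms ORs of 1.0/1.3/1.3 for medical, nursing and combined staff, the letter-sent OR is 1.118 without the interaction and 1.000-1.064 with it. Adding the Norms main effect gives 1.000. The pattern is the same.

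**The case against.** - **The analysis is supplementary.** This stands. Section 5's models are untouched, Fisher's exact test keeps the pooled contrast, and the regression is sound if no interaction enters.
- **The level can be inferred.** The protocol assumes alpha 0.05 and the SAP specifies two-sided tests. This stands; what remains open is the model in which the interactions are tested. If section 9 merely carries forward terms found significant in section 5, a uniform Norms effect enters at only 0.05, and the high entry rates above do not apply. The change of estimand after entry remains on either reading.
- **Reference dependence is conditional.** This also stands. It arises with product columns, not with one Norms slope per job type, and gender is already coded 0/1. But the version free of it moves the odds ratio furthest in (a) and (b).
- **The shifts are modest.** In (b) they are about 0.5-0.9 of a standard error, and every shifted value lies inside the starting interval. In (a) they are 0.8-1.5 standard errors, with 1 inside the interval before and after. This is fair as to size, but the shift is a change of question and not sampling error.
- **The 0/0 coding is inferred.** True, and every figure rests on it. The alternative is worse: if the factors were left missing, no-letter staff would drop out of any model containing them and the contrast could not be estimated.

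**Conclusion.** The concern holds. Followed as written, section 9 can report as its adjusted any-letter odds ratio a quantity closer to a letter without certain wording versus none, with a significance test deciding which. In the illustrations the odds ratio falls from 1.12 to 1.00-1.05 in (a) and from 1.23 to 1.14-1.18 in (b). In (b), whether the interval then includes 1 depends on coding the SAP leaves open. If wording has no effect, the expected odds ratio does not move.

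These sizes rest on 0/0 coding for no-letter staff and on assumed uptake, job mix and effects; they are not predictions for this trial. The entry probabilities also assume testing within the section 9 model. The flaw should be fixed, but it is confined to one supplementary regression.

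**What to change.** Delete the Norms and Authority interactions, and the hierarchy sentence that goes with them, from SAP section 9. Report the adjusted any-letter-versus-none odds ratio from the model with letter sent, employment type, job type and gender only.

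Do not repair the model by adding the missing main effects: the coefficient would then be the standard letter against none.

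If effect modification is of interest, Letter sent x Job type and Letter sent x Gender are the relevant terms. Label them exploratory and fit them separately from the model that gives the pooled odds ratio. With 898 controls, and under the assumptions above, power for Letter sent x Job type is about 81% for a 10-point effect confined to nurses and about 25% for 5 points.

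The cost is one edited sentence, with no extra data or staff time.
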